# 14.6 Visit 6 (All Cohorts): Procedure Assessments (On or 1 day prior to Surgical Procedure day)

The following procedures will be performed on or 1 day prior to the Surgical Procedure day:

• Vital signs

- Perform the following ophthalmic procedures, (prior to Surgical Procedure):
  - Best-corrected visual acuity by ETDRS (both eyes)
  - Slit lamp biomicroscopy (both eyes)
  - IOP (both eyes)
  - Dilated ophthalmoscopy (both eyes)
  - Color fundus photography (both eyes)
  - sdOCT (study eye only)
  - EDI-OCT optional according to investigator judgment (study eye only)
  - Ophthalmic ultrasound (study eye only)
  - Fluorescein angiography (both eyes)
  - ICG angiography optional according to investigator judgment (both eyes)
- Blood samples for clinical laboratory tests (serum chemistry, hematology, and coagulation)
- Blood sample for pharmacodynamic assessment
- Assessment of adverse events
- Record concomitant medication

#### Surgical Procedure will be performed $\geq 4$ days after the last injection:

The surgical procedure (enucleation or plaque placement) is scheduled independent of this study according to standard of care clinical management of uveal melanoma per patient's treating physician and is not a study procedure.

For Patients Undergoing Enucleation Only: After enucleation, the following samples will be obtained:

- Vitreous humor aspirate for ICON-1 and proteomic analysis
- A subset of pathology mounted slides and/or tumor block samples from the globe and tumor will be provided by the local pathology laboratory to the central laboratory for genetic tumor profiling and Exome sequencing

## 14.7 Visit 7 (All Cohorts): End of Study: 30 days ±5 days post Surgical Procedure

The following procedures will be performed  $30 \pm 5$  days after the Surgical Procedure:

- Vital signs
- Perform the following ophthalmic procedures (brachytherapy patients only):
  - Best-corrected visual acuity by ETDRS (both eyes)
  - Slit lamp biomicroscopy (both eyes)
  - IOP (both eyes)
  - Dilated ophthalmoscopy (both eyes)
  - Color fundus photography (both eyes)
  - sdOCT (study eye only)
  - Ophthalmic ultrasound (study eye only)
- Abbreviated physical examination
- Blood samples for clinical laboratory tests (serum chemistry, hematology, and coagulation)
- Blood sample for anti-drug antibody levels
- Blood sample for serum pregnancy test (women of child bearing potential only)
- Assessment of adverse events
- Record concomitant medication

If follow-up is needed after the End of Study visit, it should occur as a post-study unscheduled visit at the discretion of the Investigator. Patients with an ongoing SAE at this visit will be followed until the event is resolved or stabilized as described in Section 15.22.10

#### 14.8 Early Termination Visit

Patients who discontinue study drug or withdraw from the study prematurely will undergo an Early Termination (ET) visit. At this visit, the following will be performed:

- Vital signs
- Blood samples for clinical laboratory tests (serum chemistry, hematology, and coagulation), prior to injection of Fluorescein and ICG dye (as applicable)

- Blood sample for anti-drug antibody levels, prior to injection of Fluorescein and ICG dye (as applicable)
- Blood sample for serum pregnancy test (women of child bearing potential only), prior to injection of Fluorescein and ICG dye (as applicable)
- Blood sample for pharmacodynamic assessment (collect only if Day 1 or 1 day post Day 7 treatment PD samples were not collected following injection on Day 0 or Day 7), prior to injection of Fluorescein and ICG dye (as applicable)
- Blood sample for pharmacokinetic assessment (collect only if Day 1 or 1 day post Day 7 treatment PK samples were not collected following injection on Day 0 or Day 7), prior to injection of Fluorescein and ICG dye (as applicable)
- Abbreviated physical examination
- Perform the following ophthalmic procedures (note: ocular assessments are performed only if early termination occurs prior to Surgical Procedure):
  - Best-corrected visual acuity by ETDRS (both eyes)
  - Slit lamp biomicroscopy (both eyes)
  - IOP (both eyes)
  - Dilated ophthalmoscopy (both eyes)
  - Color fundus photography (both eyes)
  - sdOCT (study eye only)
  - EDI-OCT optional according to investigator judgment (study eye only)
  - Ophthalmic ultrasound (study eye only)
  - Fluorescein angiography (both eyes)
  - ICG angiography optional according to investigator judgment (both eyes)
- Assessment of adverse events
- Record concomitant medication

If follow up is needed after the early Termination visit, it should occur as a post-study unscheduled visit at the discretion of the Investigator. Patients with an ongoing SAE at this visit will be followed until the event is resolved or stabilized as described in Section 15.22.10.

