	
 
study for additional study-related pathology evaluation of the tumor (including ICON-1 binding, TF expression, protease activating receptors 2 (PAR2) expression, immune infiltrate, and alterations of the vasculature), genetic profiling, and Exome sequencing of the tumor. Genetic profiling of the tumor previously performed with fine needle aspiration of the tumor does not require repeated testing.
 
For brachytherapy patients: the plaque placement procedure and associated follow-up will be according to the standard of care at each site.
 
Patients (or their legally authorized representative) may choose to withdraw from the study for any reason at any time without prejudice
 
		
	Study assessments for an Early Termination Visit should be conducted in the event a patient discontinues from the study prematurely.		
Study Duration	Enrollment is anticipated to take approximately 9 months and patient participation will be up to approximately 7-8 weeks including up to 7 days for screening, and up to approximately 6-7 weeks for treatment and follow-up.		
Number of Subjects	Up to 13 patients will be enrolled in the study		
	Inclusion Criteria		
	Patients must meet all of the following criteria to be included in the study:		
	1. Verbal and written informed consent obtained from the subject or the subject's legal representative (as applicable).		
	2. Males or females of any race, $\geq 18$ years of age.		
	3. Clinical diagnosis of primary uveal melanoma involving the posterior uveal tract (choroid and/or ciliary body) in the study eye. Patients with metastatic disease are eligible.		
Study Population	4. Planned enucleation or brachytherapy for primary uveal melanoma in the study eye.		
	5. If a woman of childbearing potential (WOCBP) (i.e., not postmenopausal for at least 2 years or not surgically sterile), must have a negative serum pregnancy test at Screening, and must use adequate birth control if they have a non-surgically sterile male sexual partner throughout the study. Adequate methods of birth control include hormonal contraceptives, intrauterine contraceptive device (IUD), condom with spermicide, contraceptive sponge with spermicide, diaphragm with spermicide and cervical cap with spermicide.		

Exclusion Criteria
Patients who meet any of the following criteria will be excluded from the study:
1. Uveal melanoma in the study eye originating in the anterior uveal tract (iris).

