If an AESI occurs while the patient is at the study center and requires clinical management, the patient will remain at the study center according to the Investigator's judgment. The patient will be managed according to the routine treatment practices of the study center. The patient will complete all subsequent study visits.

All AESIs, serious adverse events, patient discontinuations and pregnancy reports must be reported to Iconic Therapeutics within 24 hours of the investigator learning of the event.

ICON-1 will be administered on Day 0 for all cohorts, and in addition on Day 7 for cohorts 2 and 3 only. Patients will return to the study center on Day 1 for a safety follow-up visit (all cohorts) and 1 day post Day 7 (cohorts 2 and 3 only). All patients will return to the clinic for safety, clinical, and imaging assessments prior to the scheduled surgical procedure. Patients will have their planned surgical procedure (enucleation or brachytherapy plaque placement) as early as 4 days after the last ICON-1 treatment, and return to the study center 30 days post-procedure for follow-up safety assessments (and ocular assessments for brachytherapy patients) and end of study visit.

Safety will be evaluated by means of occurrence of adverse events, clinical laboratory tests (serum chemistry, hematology, coagulation, and plasma anti-drug antibody levels (ADA)), vital signs measurements, abbreviated physical examinations, slit-lamp biomicroscopy, intraocular pressure (IOP), and dilated ophthalmoscopy. Pharmacodynamic and biological activity will be measured by means of BCVA by ETDRS, spectral-domain optical coherence tomography (sdOCT), color fundus photography (CFP), fluorescein angiography (FA), ophthalmic ultrasound, and optionally (according to investigator judgment) ICG angiography, and enhanced-depth imaging optical coherence tomography (EDI-OCT). Pharmacokinetic (PK) and Pharmacodynamic (PD) markers will be evaluated by means of measuring plasma concentrations of ICON-1, serum cytokine levels, circulating tissue factor (TF), immunophenotyping and circulating tumor DNA (CTDNA).

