#### 14.10 Patient Withdrawal from Treatment or Study

#### **14.10.1 Handling of Withdrawals**

Patients (or their legally authorized representative) may choose to withdraw from the study for any reason at any time without prejudice. The study assessments for the Early Termination Visit should be conducted in the event a patient discontinues from the study prematurely. If a patient withdraws from the study, he or she may not reenter the study.

The Principal Investigator or the Sponsor may withdraw a patient from the study for any of the following reasons:

- Adverse event
- Prohibited therapy (patient requires concomitant medication or a medical procedure prohibited by the protocol)
- Subject noncompliance (patient does not adhere to the requirements specified by the protocol)
- Subject improper entry (patient was enrolled in the study but did not meet the eligibility criteria)
- Subject withdrawal of consent
- Pregnancy (patient becomes pregnant)
- Lost to follow-up
- Death

At the time of withdrawal, the Principal Investigator should advise the patient of the other available options. When a patient is withdrawn from the study for any reason, the reason(s) for withdrawal will be recorded in the eCRF. For any patient who withdraws due to an AE, the reason for withdrawal must be recorded as an AE and not any other reason. Whenever possible, all patients who withdraw from the study prematurely will undergo assessments listed for the Early Termination visit.

If a patient fails to return for a scheduled visit, it is the responsibility of the Principal Investigator or designee to document all efforts to contact the patient and to determine the reason the patient did not return. If a patient cannot be contacted with 3 documented telephone call attempts,

followed by a certified letter, and does not have a known reason for discontinuation (e.g., withdrawal of consent or an AE), the reason for discontinuation will be recorded as "lost to follow-up". The date that the certified letter was mailed will be considered the date of study withdrawal.

In the event of a patient death during the study, the date of death (as listed on the death certificate) will be used as the date of study withdrawal.

It is vital to obtain follow-up data on any patient who is withdrawn due to an AE. In such cases, every effort must be made to undertake protocol-specified safety follow-up procedures.

The Medical Monitor should be notified promptly when a patient is withdrawn.

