#### 15.22.1 Definition of an Adverse Event

An adverse event (AE) is any untoward medical occurrence in a patient or clinical investigation subject administered a pharmaceutical product and which does not necessarily have a causal relationship with this treatment.

An AE can therefore be:

- Any unfavorable and unintended medical diagnosis, sign or symptom
- Any new undesirable medical occurrence or unfavorable or unintended change in a preexisting condition that occurs during or after study treatment
- Laboratory abnormality, vital sign or ophthalmic assessment that is assessed as clinically significant and different from baseline (e.g., requiring discontinuation of study treatment, specific treatment, or a change in subject management). If possible, changes in laboratory results or changes in vital signs that meet the definition of an AE should be reported as a medical diagnosis rather than as the abnormal value (e.g., "hypertension" rather than "blood pressure increased").

The following are special considerations when determining and reporting AEs:

- Whenever possible, the Investigator should group signs or symptoms that constitute a single diagnosis under a single AE term (e.g., "cough, rhinitis, and sneezing" might be grouped together as "upper respiratory tract infection").
- Pre-existing conditions are not considered AEs unless the condition worsens (increase in frequency, severity or specificity) during or following study drug administration. Fluctuations in a pre-existing condition should be assessed by the Investigator, and those that fall within the limits of expected fluctuations for the disease state, and are not assessed as worsening of the disease, should not be considered AEs. Any change assessed as clinically significant worsening of the disease from baseline must be documented as an AE.
- Elective surgery (including the planned enucleation surgery or brachytherapy, and associated inpatient hospitalization, as applicable) or routine diagnostic procedures are not considered AEs. However, an untoward medical event occurring during the pre-scheduled elective surgery or diagnostic procedure should be recorded as an AE.
- Death itself is not considered an AE; it is instead the outcome of an AE.
- Pregnancy is not considered an AE, but it is an important medical event that must be followed up as described in Section 15.22.8.

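### Section 14.8 sends patients who only stop study drug to Early Termination, so a cohort 2 or 3 patient who stops after Day 0 could be closed out before Visits 6 and 7

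*Combined protocol and SAP*

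**What the plan says.** Section 14.8 gives two triggers for the Early Termination visit: "Patients who discontinue study drug or withdraw from the study prematurely will undergo an Early Termination (ET) visit". If follow-up is needed afterwards, "it should occur as a post-study unscheduled visit at the discretion of the Investigator". The one exception is an ongoing SAE, which is followed until it resolves or stabilizes. Section 14.7 treats a patient who has finished the study in the same way: "If follow-up is needed after the End of Study visit, it should occur as a post-study unscheduled visit at the discretion of the Investigator".

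Elsewhere the trigger is narrower. The synopsis, repeated in Section 10.1, says: "Study assessments for an Early Termination Visit should be conducted in the event a patient discontinues from the study prematurely". Section 14.10.1 agrees: "The study assessments for the Early Termination Visit should be conducted in the event a patient discontinues from the study prematurely".

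The protocol does recognize stopping drug and leaving the study as different events. Section 14.10 is headed "Patient Withdrawal from Treatment or Study", and the adverse-event definition in 15.22.1 gives, as an example of clinical significance, a finding "requiring discontinuation of study treatment, specific treatment, or a change in subject management". The text under 14.10, however, deals only with leaving the study.

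The general schedule makes no exception for patients who stop drug. Section 10.1 says: "All patients will return to the clinic for safety, clinical, and imaging assessments prior to the scheduled surgical procedure". It then has patients come back 30 days after the procedure. Sections 14.6 and 14.7 assign Visits 6 and 7 to all cohorts.

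**The concern.** A patient in cohort 2 or 3 may decline or be refused the Day 7 dose and still be willing to be followed. Section 14.8 names this patient and sends them to a closing visit, after which follow-up is described as post-study. Section 10.1 expects the same patient at Visits 6 and 7. Two sites could each follow the protocol in good faith and handle the patient differently.

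Adverse events, laboratory changes and ADA are primary endpoints (Section 16.1), and every dosed patient is analysed (Section 17.1). Cohorts 2 and 3 have 3 and 5 planned patients, so one shortened follow-up is a third or a fifth of a cohort. A patient who skips the second dose because the first was poorly tolerated is one whose later safety data are especially wanted.

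**Working it through.** The plan gives no figure for this point, so the check compares provisions and does simple counts.

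**1. Who can be affected.** From Section 12.4, planned enrollment is 2 + 3 + 5 = 10 and the maximum is 3 + 4 + 6 = 13, which reproduces the stated maximum in Section 17.10. Only cohorts 2 and 3 have a second dosing day:
- planned: 3 + 5 = 8 of 10
- maximum: 4 + 6 = 10 of 13

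These are ceilings. The documents give no rate of stopping drug.

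**2. When Visit 7 would fall.** The procedure is at least 4 days after the last dose, and Visit 7 is 30 ± 5 days after the procedure. After a single Day 0 dose:
- earliest Visit 7: 4 + (30 − 5) = Day 29
- nominal Visit 7 with surgery on Day 4: 4 + 30 = Day 34
- nominal Visit 7 if the two-dose surgery date is kept: 7 + 4 + 30 = Day 41

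**3. How much earlier an Early Termination visit would be.** Section 14.8 sets no timing. If the visit falls on or before the day of surgery, then Visit 7 day − Early Termination day ≥ (surgery day + 25) − surgery day = 25 days. The nominal gap is at least 30 days. No percentage of the treatment-emergent period is given, because that would need an assumed visit day and because Sections 15.22.1 and 17.6 define treatment-emergent differently (one ends 30 days after the last dose, the other gives no end).

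**4. What is collected under each reading**, for a patient who stops after Day 0, has the closing visit before surgery, and already gave the Day 1 samples:

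| Item | Closed out under 14.8 | Visits 6 and 7 kept |
|---|---|---|
| Scheduled visits after the closing visit or drug stop | 0 | 2 |
| Last scheduled adverse-event enquiry and laboratory tests | Early Termination | Visit 7, Day 29 or later |
| Post-dose ADA samples in the flowchart | 1, early | 1, Day 29 or later |
| Eye examination after brachytherapy | none | Visit 7 |
| Pre-procedure PD and ctDNA sample (15.19) | not drawn: 14.8 takes PD only if the earlier post-dose sample was missed | Visit 6 |

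The ADA row follows Appendix B. Section 15.18 gives ADA times of Week 2, Week 8 and Early Termination, which do not match the flowchart. Either way, an early closing visit removes the late sample.

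**5. Which patients other clauses already protect.**
- A patient with an AESI that occurs and is managed at the center completes all later visits (synopsis, 10.1).
- Every effort is made at safety follow-up for a patient withdrawn because of an adverse event (14.10.1).
- Ongoing SAEs are followed (14.8, 15.22.10).
- New related SAEs that the investigator learns of within 30 days after the last scheduled contact are reported (15.22.11).

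This leaves voluntary drug stops, and stops for other adverse events without formal withdrawal, including an AESI that begins away from the center. Non-serious events are followed only to study exit (15.22.10).

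**The case against.** The best reply is that 14.8 has a loosely worded trigger and nothing more. The requirements for Visits 6 and 7 are unconditional, and the words about post-study visits fit patients who have left the study, which is how the synopsis, 10.1 and 14.10.1 use Early Termination. Section 15.22.8 supports this: for a confirmed pregnancy it specifies both a permanent drug stop and withdrawal from the study, and the second step would be redundant if the first already ended participation. There is oversight too: discontinuations reach the sponsor within 24 hours (10.1), and unscheduled safety visits are allowed while a patient is enrolled (14.9). Section 14.10.2 lets patients who leave before the pre-procedure evaluation be replaced, which eases the tension with the rule in 12.4 that all patients at a dose level complete that evaluation.

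Much of this stands, and it rules out several stronger readings that a reader might infer:
- That 14.8 cancels Visits 6 and 7. No sentence does so; early close-out is an inference from its wording.
- That 14.8 is the only visit rule for such a patient. Sections 10.1, 14.6, 14.7, 15.19 and Appendix B apply as well.
- That vitreous and tumor samples are lost. Sections 14.6 and 15.20 tie them to enucleation, and Appendix B makes them mandatory.
- That ADA data are halved. A patient who completes the study also has one post-dose sample in the flowchart; what changes is its timing.

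It does not remove the conflict. Section 14.8 names patients who stop drug, gives them a closing visit and describes what follows as post-study. Replacement helps the escalation decision but does nothing for the follow-up of the patient who stopped.

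**Conclusion.** The point holds as a conflict between a stated rule in 14.8 and the rest of the protocol, with a possible loss of late primary-endpoint safety data. Severity is minor. The loss arises only if a site applies 14.8 as worded to a patient who stops drug, stays willing to be followed, and is not covered by the AESI, adverse-event withdrawal or SAE clauses. The number of such patients is unknown and may be zero. For each one whose closing visit falls before surgery, the last scheduled safety contact moves forward by at least 25 days. No escalation rule, endpoint definition or analysis set is affected.

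**What to change.** In Section 14.8, limit both the Early Termination visit and the sentence on post-study unscheduled visits to patients who withdraw from the study. This brings 14.8 into line with the synopsis, 10.1 and 14.10.1. Then add:

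> *Patients who stop ICON-1 but do not withdraw from the study remain in the study and complete Visits 6 and 7 as scheduled (including post-enucleation samples where applicable); any safety assessment needed at the time of the drug stop is done as an unscheduled visit. Confirmed pregnancy is handled under 15.22.8.*

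Keeping the full Early Termination assessments at the drug stop and adding Visit 6 is not advised, because it could repeat angiography, imaging and blood draws shortly before surgery.

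The cost is one qualifier and one short addition to 14.8. There is no new visit type and no change in sample size, and the surgery is standard of care. The burden is one or two already planned visits for the few patients who stop drug.

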# **16 STUDY ENDPOINTS**

#### **16.1 Primary Endpoints**

Safety as measured by:

- Occurrence of ocular and systemic serious adverse events and adverse events
- Changes in standard clinical laboratory tests (serum chemistry, hematology, coagulation) and ADA levels
- Changes in vital signs and physical and ophthalmic examinations

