#### SE=Study Eye, OU=Both Eyes

 If there is study drug available at the clinical site, Screening assessments may be conducted on same day as Baseline visit (Day 0), prior to enrollment and intravitreal injection. Informed consent must be obtained before any study related screening activity or treatment is undertaken that is not part of routine care.  Cohort 1 does not have Visit 4 or 5; the next visit after Visit 3 is Visit 6.

Height and weight measured at Screening only.

 IOP measured using routine practice with a calibrated contact tonometer. For study eyes, IOP will be measured pre and post injection(s).

 Blood samples for PK and PD assessments will be drawn before and 4 hours  $\pm 1$  hour post injection.

 At Early Termination, blood samples for PK and PD assessments will be drawn if Day 1 PK/PD blood samples were not collected following injection on Day 0.

 The surgical procedure is scheduled independent of this study according to standard of care clinical management of uveal melanoma per patient's treating physician and is not a study procedure.

 Following enucleation, vitreous humor will be collected for ICON-1 and proteomic analysis of TF and other cytokine levels. In addition to the pathology standard procedures of the clinical site, the study-related pathology slides and/or tumor block sample will be prepared and shipped to a central study laboratory for additional evaluations of the tumor (TF expression, ICON-1 binding, immune infiltrate, genetic profiling, and Exome sequencing). Genetic profiling of the tumor previously performed with fine needle aspiration of the tumor does not require repeated testing.

 Ocular assessments for brachytherapy patients only.

 Ocular assessments at early termination visit only if early termination occurs prior to surgical procedure.

Study Day	Screening  Day -7 to 0	Baseline Treatment Day 0	Day 1	Treatment Day 7 ±2 days	1 day post Day 7 Treatment	Procedure Assessments (On or 1 day prior to Surgical Procedure  day)	End of Study 30 days ±5 days post Surgical Procedure	Early Termin- ation
Visit	1	2	3	4	5	6	7	ЕТ
Demographic Data	Х							
Medical/Ocular/Surgical/ Medication History	Х							
Vital Signs	Х	Х	Х	Х	Х	Х	Х	Х
Serum Chemistry, Hematology and Coagulation Blood Samples	Х			Х		Х	Х	Х
Anti-drug Antibody levels (ADA)	Х						Х	Х

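### Early Termination after the procedure omits the eye examinations for brachytherapy patients too, although Visit 7 requires them

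*Combined protocol and SAP*

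**What the plan says.** Section 14.8 lists the eye examinations for the Early Termination visit and qualifies the whole list: "ocular assessments are performed only if early termination occurs prior to Surgical Procedure". Footnote 10 in Appendix A (cohort 1) says the same, "Ocular assessments at early termination visit only if early termination occurs prior to surgical procedure", and footnote 10 in Appendix B (cohorts 2 and 3) repeats it.

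The surgical procedure is not only eye removal. Section 10.1 speaks of the "planned surgical procedure (enucleation or brachytherapy plaque placement". For Visit 7 the plan does separate the two groups. Section 14.7 opens its list with "Perform the following ophthalmic procedures (brachytherapy patients only" and then names seven procedures, footnote 9 in both appendices makes the same restriction, and section 10.1 describes the visit as "follow-up safety assessments (and ocular assessments for brachytherapy patients".

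Section 16.1 includes "Changes in vital signs and physical and ophthalmic examinations" among the primary endpoints. The safety measures in section 10.1 include "abbreviated physical examinations, slit-lamp biomicroscopy, intraocular pressure (IOP), and dilated ophthalmoscopy". Section 15.10 asks for IOP at every study visit, in both eyes except after injections and at the one-day post-treatment visits.

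**The concern.** After enucleation there is no study eye left to examine, so the restriction in section 14.8 makes sense for those patients. After plaque placement the eye is still there, and the plan wants it examined about a month later. As written, a brachytherapy patient who completes the study has a closing eye examination, and one who leaves after plaque placement has none. No reason is given for the difference.

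Withdrawal may be linked to how the eye is doing. If so, the missing examination would not be missing at random, and in a trial of at most 13 patients it would be visible in the safety tables. The documents give some reason to look at the eye later than a few days after dosing. Section 8.2 reports ocular inflammation in mini-pigs on repeat dosing, most evident after the second dose, although the protocol suggests that this is species-specific. Section 8.3 reports one drug-related vitritis at 300 µg in the earlier Phase 1 study.

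**Working it through.** The plan states no figure to reproduce. The check compares schedules and adds up visit windows.

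**1. Eye procedures after plaque placement, brachytherapy patient**

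| Procedure | Role in section 10.1 | Visit 7 (14.7) | Early Termination after procedure (14.8) |
|---|---|---|---|
| Slit lamp | safety | yes | no |
| IOP | safety | yes | no (but 15.10 implies yes) |
| Dilated ophthalmoscopy | safety | yes | no |
| BCVA | activity | yes | no |
| Color fundus photography | activity | yes | no |
| sdOCT | activity | yes | no |
| Ultrasound | activity | yes | no |

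The totals are 7 against 0. Of the 7, 3 are safety measures and 4 are pharmacodynamic or biological activity measures. No eye visit is scheduled between the procedure and Visit 7, so one set is the most that an affected patient can miss.

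**2. Timing**

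Let L be the day of the last dose.

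- Earliest procedure (section 10.1, "as early as 4 days after the last ICON-1 treatment"): L + 4.
- Visit 6, on the procedure day or the day before (section 14.6): L + 3 or L + 4.
- End of the TEAE window (section 15.22.1): L + 30.
- Days in the window after the last scheduled eye examination: 30 − 4 = 26, or 30 − 3 = 27.

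A later procedure shortens this gap. Visit 7 would fall at 4 + 30 ± 5, that is L + 29 to L + 39. A completer therefore also goes most of this window without a scheduled eye examination, but has one at the end that can show what happened in between. The patient who terminates early does not.

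**3. Whether another provision fills the gap**

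- Follow-up after Early Termination (14.8) and unscheduled visits (14.9) are at the investigator's discretion.
- For withdrawals due to an adverse event, section 14.10.1 asks for every effort, but towards the procedures that the protocol specifies. After the procedure, section 14.8 excludes eye examinations from these.
- The abbreviated physical examination (15.7) covers the eyes under HEENT but is not an ophthalmic examination.
- Section 17.3 offers no missing-data method other than replacement. Section 14.10.2 limits replacement to patients who leave before the pre-procedure evaluation.

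**4. Number affected**

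The expected number would be patients enrolled × brachytherapy share × probability of withdrawal between plaque placement and Visit 7. Only the first factor is given (up to 13: 3 + 4 + 6). The product cannot be computed and may be zero.

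**The case against.** The best defence is that little is lost. Visit 6 provides a full eye examination after all dosing. Adverse events are still assessed at Early Termination, AESIs and SAEs are reported within 24 hours, and SAEs are followed until resolved or stable. Brachytherapy follow-up continues under each site's standard of care. Dosing is over by then, so only withdrawal during about one month matters. The analysis is descriptive (section 17.1). Findings after plaque placement are hard to attribute to ICON-1, since section 8.1 itself names retinopathy, cataract, glaucoma and vision loss as complications of radiation.

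Most of this stands, and it limits the size of the point. It does not remove it, because none of these provisions requires a closing eye examination, and Visit 7 shows that the sponsor wants one despite the attribution problem.

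A reader might infer that primary ocular safety data are lost in general, or that escalation decisions are weakened. The documents do not support that. DLT review rests on the pre-procedure assessment (sections 12.4 and 13.2), and only three of the seven missing procedures are classed as safety measures. A reader might also size the gap as the share of study time after the procedure, or as one patient's share of a cohort. The first measures calendar time, not lost data, and the second presumes an affected patient.

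**Conclusion.** The inconsistency is real and worth correcting, but small. Sections 14.7 and 10.1 and footnote 9 treat the retained eye as examinable after plaque placement; section 14.8 and footnote 10 do not. For IOP, section 15.10 conflicts with the exclusion, so the documents disagree there rather than uniformly omit the measurement.

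For each brachytherapy patient who withdraws between plaque placement and Visit 7, one closing examination set is unscheduled. The gap of 26 to 27 days assumes the earliest permitted procedure and is an upper limit. How many patients this concerns is unknown. The conclusion rests on the text as written; sites may examine such patients anyway, but the plan does not ask them to.

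**What to change.** In section 14.8 and in footnote 10 of both appendices, say that the eye examinations are done when termination precedes the procedure, and that a brachytherapy patient who terminates after plaque placement has the Visit 7 eye set. The exemption then covers only patients whose eye has been removed. Reconcile section 15.10 with this wording, and with footnote 9, because read literally it asks for IOP in both eyes at Visit 7 even after enucleation.

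The cost is one sentence in three places and a matching edit to section 15.10. The patient has no examination beyond those planned for Visit 7. Dosing, escalation and clinical management do not change.
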